Scientists. I will disseminate these findings to scientists with interests in early childhood development and education as well as nutrition and obesity prevention. I will attend the premier conference in nutrition, child development, and implementation science. I will also submit findings for publication to leading journals in the field such as *Early Childhood Research Quarterly*, *Child Development*, *Appetite*, and *Journal of Nutrition Education and Behavior*. I will also share abstracts and publications with academic listservs and professional social networking sites on which I am a member.

Community Stakeholders. Early educators are a primary stakeholder in the findings of this research as well as directors and principals at agencies and schools. I will share back findings of all stages of the project to participants and partnering agencies. I will also reach stakeholders through presentation at local conferences with an early education focus. In addition to presentation at in-person sessions, I will prepare Fact Sheets highlighting key findings to distribute from the booth that our department hosts at this conference each year. This will increase the reach of the dissemination beyond those that attend a presentation session. I will also send a thank you letter to teachers involved in both the secondary data and primary data portions of this project which will summarize our findings and next steps.

Study Title: Developing and Testing Implementation Strategies for Evidence-Based Obesity Prevention in Childcare
PI: [name]
Institution: University of Arkansas for Medical Sciences
Support: NIH K01 DK110141-01, Arkansas Biosciences Institute (FUNDED)
NIGMS COBRE Center for Childhood Obesity Prevention (FUNDED)

References

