To execute these aims, we will use innovative methodologies including an explanatory mixed methods approach (Aim 1), a stakeholder-driven Evidence-Based Quality Improvement (EBQI) process (Aim 2), and a Hybrid Type 3 implementation design using formative evaluation (Aim 3). We expect that implementation strategies developed with stakeholders will lead to improved implementation fidelity. We will test the hypothesis that improved WISE fidelity is positively related to child outcomes (e.g., child fruit and vegetable intake, BMI). This research will provide critical knowledge on the value of investments in implementation support strategies to existing obesity prevention interventions.

Background and Rationale

Overweight and obese children are at 5-times greater risk for developing diabetes and at 3-times greater risk for hypertension and high triglycerides in adulthood.⁴ Concurrent health issues include asthma, metabolic risks, depression, and attention deficit hyperactivity disorder.^{5,6} In spite of some recent progress, the prevalence of childhood obesity is still alarming, particularly for children of lower socioeconomic status.⁷ For example, 14.2% of 2 to 4 year olds in low-income families in Arkansas (AR) are obese which is higher than the national average for this age range.⁸ Further, recent data show that Arkansas has the highest adult obesity rate in the nation (35.9%).⁹ Prevention efforts in this high-risk area are clearly warranted.

Given that families impacted by poverty often access subsidized childcare, childcare provides a critical setting to address socioeconomic disparities in obesity. Children may eat over half of their dietary intake in this setting, up to 540 meals and snacks per school year.¹⁰ This is notable because young children's eating habits are more attributable to environmental factors than genetics.¹¹ The overarching goal of this study is to apply principles of Implementation Science (e.g., formative evaluation, enhanced facilitation) to support the uptake and sustainability of an evidence-based interventions (EBIs) for obesity prevention and nutrition promotion in childcare.

Study Title: Developing and Testing Implementation Strategies for Evidence-Based Obesity Prevention in Childcare
PI: [name]
Institution: University of Arkansas for Medical Sciences
Support: NIH K01 DK110141-01, Arkansas Biosciences Institute (FUNDED)
NIGMS COBRE Center for Childhood Obesity Prevention (FUNDED)

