A primary goal of this study is to improve use of evidence-based obesity prevention in childcare through development of effective implementation strategies. We will enhance knowledge of how to improve implementation, fidelity, and sustainability in these under-studied locations. Childcare shares some contextual similarities with other locations where implementation research has taken place (e.g., schools and other contexts where “paraprofessionals” provide health-related services); however, we don’t know whether lessons learned apply to childcare. Ultimately, improvements in evidence-based obesity prevention in childcare have the ability to impact 11 million children under age 5 in the US annually.³⁶ It is therefore imperative that we develop and test strategies to maximize implementation and sustainability of these practices.

Objectives

This proposal proposes the following aims:

Specific Aim 1. Identify factors associated with degree of fidelity in a previously developed and tested *basic implementation strategy* of WISE. An explanatory mixed methods approach will use secondary data to identify positive deviance and implementation failures among ECEs in a previous WISE implementation study that observed notable variability in fidelity to best practices for obesity prevention. ECEs from the prior study will be identified from quantitative fidelity observations and invited to participate in qualitative interviews to determine contextual and individual barriers and facilitators to effective implementation.

Specific Aim 2. Develop an *enhanced implementation strategy* to support uptake of the WISE intervention using stakeholder input. Based on results from Aim 1, an Evidence-Based Quality Improvement (EBQI) process¹⁸ will be used to engage stakeholders to develop implementation support strategies consistent with an implementation framework (i-PARiHS) and matched to identified barriers/ facilitators.

Specific Aim 3. Pilot test the impact of the *enhanced implementation strategy* on implementation and child health outcomes using continuous formative evaluation. We will determine whether the enhanced strategy is feasible, acceptable, and demonstrates improved implementation, fidelity, and sustainability using a Hybrid Type 3 implementation design.¹ Further, we will test the hypothesis that better WISE fidelity is positively related to child outcomes (e.g., child fruit and vegetable intake, BMI).

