Aim 3. We will use a Type 3 Hybrid Design to test the effectiveness of the enhanced implementation strategy (i.e., facilitation) on uptake while also assessing impacts of the intervention on child outcomes. We expect that the effectiveness of WISE on child outcomes will vary by the level of implementation fidelity, and a Hybrid 3 design allows for us to explore this hypothesis (in a preliminary fashion in the proposed pilot study, but in a definitive fashion in the subsequent R01).

RE-AIM provides an evaluation framework to assess key aspects of intervention programs implemented in real-word settings. See Table 1 for a summary of outcome measures that align with RE-AIM. Reach will be reflected by teacher report of the number of realized opportunities for WISE lessons divided by the number of possible opportunities (target = 4 opportunities per child per month). Adoption will be

measured using teacher reports of the number of WISE handouts distributed (target = 2 per child per month), teacher report of the number of WISE lessons and activities presented each month, and assessment of food purchase records to assess frequency of purchase of WISE foods. Further, we will modify and use The Organizational Readiness to Change Assessment (ORCA)⁸⁵ as developed for use with the i-PARIHS framework to assesses change commitment (e.g., We value this change) and change efficacy (e.g., We can keep the momentum going) both prior to and during implementation. For Implementation, our WISE fidelity measure will be used across the school year. The WISE fidelity instrument (See WISE fidelity) is rated on a 1 to 4 scale with 4 representing the highest level of fidelity. Each core component is assessed with 2 items. Average fidelity scores above 3 are considered to reflect adequate fidelity on a component. Additionally, overall scores on the fidelity form are created by summing scores across items (range = 0 – 32). Inter-rater reliability of 85% will be ensured. Finally, acceptability and feasibility²⁶ will be assessed through semi-structured

Table 1. Outcome Measures for Hybrid Trial

Construct	Measures
Reach	Number of ECEs/students impacted
Effectiveness	Child FFQ; Child BMI; Child RRS scan
Adoption	Food purchase records reflecting the number of WISE lessons completed; ORCA
Implementation	WISE fidelity, acceptability, feasibility
Maintenance	Number of teacher maintaining/increasing in fidelity after 6 months

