Secondary outcomes will include those related to impacts of the program on children (i.e., Effectiveness). All families complete a Family Map Inventory (FMI)⁸⁶ for fall and spring assessment of family strengths and needs. For this study, the FMI will include a Food Frequency Questionnaire to assess consumption of WISE foods. BMI is a required twice-yearly, federal assessment for Head Start children. An anonymous record review of these data will provide a comparison of impacts on child diet between the basic and enhanced implementation conditions. Further, we will collect Resonance Raman Spectroscopy (RRS) scans from children with equipment leased from NuSkin. RRS is a promising alternative for measuring biomarkers where carotenoid levels are measured by an optical scan of the palm.^{87,88} Carotenoids (i.e., plant pigments) are

Study Title: Developing and Testing Implementation Strategies for Evidence-Based Obesity Prevention in Childcare

PI: [name]

Institution: University of Arkansas for Medical Sciences

Support: NIH K01 DK110141-01, Arkansas Biosciences Institute (FUNDED)

NIGMS COBRE Center for Childhood Obesity Prevention (FUNDED)

phytochemicals that provide the bright colorings to vegetables.⁸⁹ When ingested, carotenoids become biomarkers for dietary habits, evident in the makeup of cell tissues including the skin.⁹⁰ RRS measurements are reflective of dietary intake over the previous four weeks. RSS scans are sensitive to detecting individual differences of carotenoid levels^{91,92} and experimentally initiated changes.^{93,94}

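### Aim 3 promises a test of WISE fidelity against child outcomes, but the stated models name no fidelity term, so the hypothesis gets no coefficient or interval

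*Combined protocol and SAP*

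**What the plan says.** The Abstract states: "We will test the hypothesis that improved WISE fidelity is positively related to child outcomes". Objectives, Specific Aim 3, repeats the promise: "we will test the hypothesis that better WISE fidelity is positively related to child outcomes (e.g., child fruit and vegetable intake, BMI"). Study Design and Procedures, Aim 3, expects the effect of WISE on children to depend on how faithfully it is delivered. It says the question will be explored "in a preliminary fashion in the proposed pilot study, but in a definitive fashion in the subsequent R01". The same section sets the rank of the child measures: "Secondary outcomes will include those related to impacts of the program on children (i.e., Effectiveness").

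Data Analysis, Aim 3, is the only quantitative analysis text for this aim. It specifies multi-level models with fixed effects for arm and time, and random effects for child clustering by classroom and repeated observations by teacher. It then says the analysis yields the variance in child outcomes due to implementation, which it equates with level 2. In Table 1 the Implementation row reads "WISE fidelity, acceptability, feasibility".

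The fidelity instrument "is rated on a 1 to 4 scale with 4 representing the highest level of fidelity". "Each core component is assessed with 2 items", component averages above 3 count as adequate, and "overall scores on the fidelity form are created by summing scores across items (range = 0 – 32"). Observations are made in Fall, Winter and Spring.

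**The concern.** The promise is a directional statement about a named predictor, and the listed model terms do not include that predictor. If the analysis follows them, a hypothesis that appears in both the Abstract and Aim 3 ends with no coefficient, interval or direction, and ordinary differences between classrooms could be reported as an implementation effect. If a fidelity predictor is meant but unwritten, several choices stay open until the data are seen: component average, above-3 threshold or summed score; which of three waves; which covariates. For BMI, a positive relation does not by itself say whether higher or lower values are expected.

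**Working it through.** The plan gives no sample size, power, SD or ICC for this hypothesis, so there is no stated figure to reproduce.

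**1. Promise against model.**

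| Needed to test the hypothesis | Stated in Data Analysis, Aim 3? |
|---|---|
| A fidelity predictor of child outcomes | No; only arm and time are fixed terms |
| Which fidelity score | No |
| Which wave or combination of waves | No |
| A signed estimate with an interval | No; only a level-2 variance |

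The arm coefficient does not fill the gap. It contrasts two implementation strategies, and classrooms within one arm can differ widely in fidelity.

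**2. Variance has no direction.** If the outcome changes by b SD per SD of classroom fidelity, fidelity adds b² to classroom variance: (+0.2)² = (-0.2)² = 0.04.

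A simulation shows the same thing (38 classrooms of 22 children, 5,000 runs per case). Assumptions: one post-implementation measurement, ICC 0.05, fidelity independent of arm, no arm effect, and fidelity explaining half the classroom variance when an association exists. With arm only, mean level-2 variance was 0.0505, 0.0501 and 0.0503 for a positive, negative and absent association. Adding fidelity halved it to 0.0253 for both signs. So even a variance-explained figure cannot show a positive relation. The fidelity coefficient recovered the sign (+0.159 and -0.158; true values ±0.158).

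**3. Precision of a fidelity coefficient (illustration).** From the plan: 38 classrooms, 12 sites and up to 820 children, so 820/38 = 21.58 per classroom. Assumed: outcome SD 1, fidelity scaled to SD 1, all 820 children measured, no gain from Fall adjustment.

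Variance of a classroom mean: v = ICC + (1 - ICC)/21.58. This is 0.0654, 0.0940 and 0.1417 at ICC 0.02, 0.05 and 0.10.

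With arm and fidelity in the model, let a be the share of fidelity variance explained by arm. Then the half-width is t(0.975, 35) × √(v / (36(1 - a))), with t = 2.030. For example, at ICC 0.05 and a = 0: 2.030 × √(0.0940/36) = 0.104.

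| a (assumed) | ICC 0.02 | ICC 0.05 | ICC 0.10 |
|---|---|---|---|
| 0 | 0.087 | 0.104 | 0.127 |
| 0.25 | 0.100 | 0.120 | 0.147 |
| 0.50 | 0.122 | 0.147 | 0.180 |

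With site fixed effects, df = 38 - 12 - 1 - 1 = 24 and the half-width is t(0.975, 24) × √(v/(25w)), where w is the assumed share of fidelity variance lying within sites. At w = 1 it is 0.106, 0.127 and 0.155; at w = 0.5 it is 0.149, 0.179 and 0.220. These figures again take arm to explain none of the fidelity variation, and they require both arms within sites. They widen by 1/√0.75 = 1.15 or 1/√0.5 = 1.41 if arm explains 25% or 50%.

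**4. Score range.** A sum of items rated 1 to 4 cannot reach 0. With two items per component and the four components given in Data Analysis, Aim 1, there are 8 items and the range is 8 × 1 = 8 to 8 × 4 = 32. A range of 0 to 32 does fit the different Aim 1 score, a count over 4 components × 8 observations.

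**The case against.** The strongest reply is that a reader might infer too much from the level-2 sentence, namely that the plan rules out a fidelity predictor. The documents do not support that. Speaking of variance accounted for is normal language for a level-2 predictor, Table 1 puts fidelity first under Implementation, and the list of model terms is not said to be complete. This stands as a statement about possible intent. It does not close the gap: the same Table 1 row holds acceptability and feasibility, no section names the predictor, and variance explained still has no sign.

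Two other stronger readings also fail. A reader might see a contradiction between promising a test and calling it preliminary; a preliminary test is still a test. A reader might take 8 to 32 as the only possible range and as damaging the analysis. But the component count comes from the Aim 1 text, the fidelity form is not in the documents, and a misprinted minimum would not change a regression on the score.

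It is also fair to say that the consequence is limited, because the randomised arm comparison is untouched, and that extra models add multiplicity. Both points stand and shape the fix.

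**Conclusion.** The concern holds as a gap in a secondary, preliminary analysis that should be closed. Followed as written, the stated terms cannot answer the fidelity hypothesis, because level-2 variance is neither specific to fidelity nor directional. This conclusion rests on the text and on the algebra of variance, not on the assumed ICCs.

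The precision figures are illustrative: about 0.09 to 0.13 outcome SD per SD of fidelity if arm explains none of the fidelity variation, 0.10 to 0.15 if it explains 25%, and 0.12 to 0.18 if it explains 50%. The first range should not be read as the expected precision, since the enhanced strategy is meant to move fidelity. Site terms widen all of these. Whether site fixed effects can be fitted with arm is uncertain, because Study Design and Procedures, Aim 3, describes classroom randomisation but also refers to whole sites as belonging to the enhanced condition. The figures also count every child and ignore measurement error in fidelity; only the lack of credit for Fall adjustment works the other way. The estimate can only be exploratory. The score-range mismatch is minor.

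**What to change.** Keep the arm comparison as its own model. Then:

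- Add one exploratory model for each of FFQ, BMI and RRS: Spring value on Fall value, arm and one prespecified classroom fidelity score (for example the mean over observed waves), with a classroom random effect. Use the classroom's Fall mean if a child's two records cannot be linked; the plan calls the record review anonymous yet describes a matched design.
- Show a version without arm, because adjusting for arm removes the fidelity difference the strategy is meant to create. Allow for site as a sensitivity check, using site fixed effects only if both arms occur within sites.
- Report the fidelity coefficient with its interval, and state the expected direction for each outcome. Label it a non-randomised exploratory association from at most 38 classrooms across three outcomes, with no confirmatory claim.
- Reword the level-2 sentence so that classroom variance is not equated with implementation. If a fidelity predictor was always intended, write it out in these terms.
- Reconcile the 0 to 32 range with the 1-to-4 items.

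The cost is 3 outcomes × 3 versions = 9 fits on data already planned, a join of fidelity and child records by classroom, and a few sentences. The downside is an imprecise, non-randomised estimate.

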Aim 2. We will use EBQI to (1) match barriers and facilitators to WISE implementation with potential strategies, (2) tailor strategies to the early childhood context, and (3) finalize the enhanced implementation strategy for WISE. The EBQI Panel will include teachers and directors from representative sites that will implement the enhanced strategy in Aim 3. We will include at least one teacher from previous WISE implementation to have an expert advisor role, providing feedback on feasibility and acceptability of potential enhanced implementation interventions based on prior experiences. We will also recruit parents to inform (a) potential improvements to enhance the link between the classroom and home and (b) strategies to improve assessment of impacts on WISE for future studies (e.g., parent recruitment strategies, collection of genetic/ biological data for possible future moderator/mediator analyses). We expect to recruit an EBQI panel of 10 stakeholders. The EBQI panel will review the data on the evidence-based practices, examine the data collected in Aim 1, and outline suggested implementation strategies. The group will work until we have a mutually agreed-upon, locally-adapted (if necessary) WISE intervention and a set of implementation interventions/tools (our “enhanced” implementation strategy) with accompanying steps on how to deploy them.

We will employ strategies to provide structure to the EBQI process. For example, a concept mapping approach invites stakeholders to rate proposed strategies in regards to their importance and feasibility on a Likert scale (1=not important/feasible, 5 = extremely important/feasible). This approach provides quantifiable information, promotes efficient collection of input, and provides a basis from which to probe the EBQI panel. Meetings are anticipated to last 1-2 hours. We will audio record the

Study Title: Developing and Testing Implementation Strategies for Evidence-Based Obesity Prevention in Childcare

PI: [name]

Institution: University of Arkansas for Medical Sciences

Support: NIH K01 DK110141-01, Arkansas Biosciences Institute (FUNDED)

NIGMS COBRE Center for Childhood Obesity Prevention (FUNDED)

meetings to facilitate later review. Participants will receive \$50 for service at each of the 8 sessions of the panel.

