In addition to these measures collected through the K01 study, the COBRE project will support the addition of ECE Feeding Assessments at mealtimes and a baseline assessment of center climate and context. The K01 protocol only included support to assess fidelity to this core component at WISE lessons, not mealtimes. However, it is possible that ECEs' adoption (or lack thereof) of positive feeding practices at mealtimes may impact the overall effect of WISE on child outcomes. We will add two assessments of ECE Feeding Practices: Table Talk⁷⁹ and the Food Intake module of the Building Mealtime Environments and Relationships (BMER)⁸⁰ inventory. Both measures are suited for live observations to record actual ECE behavior. Table Talk quantifies ECEs' feeding communications and captures the full range of practices (i.e., not prone to ceiling effects). It captures feeding communications that are detrimental (e.g., comments that pressure children to eat more, hurry children to finish, coerce children to eat certain foods) and those that are evidence-based (e.g., direct to internal cues, support food exploration). The Food Intake module of BMER captures adult interactions that support or undermine self-regulation at meals (e.g., "Adults do not praise children for cleaning their plates."). These baseline measures will be collected in the Spring of 2018 across 4 months (Feb- May) (See Combined Mealtime Observation Forms). We will collect three assessments in each classroom to best account for potential variability due to time of year or the menu served. Prior to classroom observations, each teacher will be invited to complete a one page (front and back) survey about characteristics of her center (See Pre-WISE Context Measure). This information will be used to inform stratified randomization to treatment conditions (basic or enhanced).

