An additional secondary outcome of interest is the cost required to deliver the enhanced implementation support. Through the EBQI process, we determined the enhanced condition sites will each have a site-level champion. This champion will be a local leader in WISE implementation. Champions will receive an additional 3 hours of training to equip them to serve in this role. Champions will be supported by external facilitators from the WISE staff. The facilitators will meet with each champion in person at least once per month. Related to estimating the costs of this strategy, facilitators will track their contacts with sites (See Facilitation Log). We will also request tracking of efforts by site champions. (See Champion Log). Finally, we will ask all teachers to report monthly on their use of lesson and enhanced support materials (See Teacher Material Report). Data will be collected either through a secure RedCap Server or using paper and pencil.

Our partnering Head Start agency has 12 sites with 38 classrooms. Classrooms will be randomized to participate in either the basic (i.e., control) or enhanced implementation of WISE. Sites are all within Pulaski County and have a similar demographic make-up of ECEs and families. All families served meet the federal guideline for poverty (e.g., an annual income of \$24,250 for a family of 4). All ECEs will receive basic implementation supports (6-hour training at beginning of school year and monthly newsletter). Those randomized to the enhanced condition will receive the additional package of implementation support strategies developed in Aim 2 on a schedule agreed upon by the EBQI panel (e.g., monthly). These will be delivered by the PI or the research assistant. For both groups, we will collect child data before and after implementation. This will provide us with a matched design to assess comparative effectiveness. For both groups, the 6-hour training will be conducted in collaboration with the USDA-funded Team Nutrition project at UAMS (IRB # 206442). Their exempt training evaluation protocol will be in place. We will extract records from their database specific to our UAMS Head Start attendees, link with other study records, and then de-identify data using our coded ID system.

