Aim 1. 37 Head Start educators and directors will complete one-on-one, open-ended interviews. The educators will be selected based on secondary data from WISE fidelity observations collected in a previous study. These data were collected with consent of the educators. Based on total fidelity scores, the top and bottom 15 educators will be invited to provide input on the barriers and facilitators to their success. Directors from participating agency will be invited to provide their input on the same topic. Once selected, educators will be contacted via their center's phone number and invited to participate. We will provide information about the study over the phone, and educators will have the opportunity to schedule an interview. Teachers will be provided an incentive of \$25 for participation in the interviews.

Aim 2. In Aim 2, we will engage key community stakeholders to serve on our Evidence-Based Quality Improvement (EBQI) panel and provide input on development of an enhanced implementation strategy for WISE. This process will review the existing scientific evidence and data from Aim 1 with the EBQI panel to solicit stakeholder input on how best to support WISE implementation. We will recruit stakeholders from:

- (a) sites that will implement WISE in Aim 3,

Study Title: Developing and Testing Implementation Strategies for Evidence-Based Obesity Prevention in Childcare
PI: [name]
Institution: University of Arkansas for Medical Sciences
Support: NIH K01 DK110141-01, Arkansas Biosciences Institute (FUNDED)
NIGMS COBRE Center for Childhood Obesity Prevention (FUNDED)

(b) sites that have previously implemented WISE, and

(c) parents served by Head Start.

EBQI sessions will be audio recorded to allow for review of content covered in each session and to allow for rapid coding of the reactions of the EBQI panel. These data will be collected anonymously. Panel members may also be asked to complete survey instruments to provide quantitative input on proposed strategies. The identity of EBQI members will not be included in reports or manuscripts. Each panel member will receive \$200 for service on the panel. We expect to engage approximately 10 stakeholders in the panel and to meet in person 6-8 times.

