Aim 3. 38 classrooms from our partnering Head Start agency will be randomized to implement the basic WISE strategy used in previous studies or the enhanced WISE strategy developed in Aim 2. Because the program is now adopting the WISE curriculum in all agency classrooms, WISE lessons are a part of normal educational activities. As such, we request a waiver of consent for these observations. In addition, 10 educators will be randomly selected and invited to provide feedback on feasibility and acceptability through semi-structured, open-ended interviews twice during the school year. We are requesting waiver of consent for these interviews as they would be the only document identifying teachers as participants in interviews. We will collect verbal consent on our audio recording. Teachers, directors, and champions will be paid \$25 for the interviews as they will take place outside of center hours.

Additionally, to assess comparative impacts on children, we will record review Body Mass Index (BMI) and Food Frequency Questionnaire (FFQ) data from the agency records at the beginning and end of the school year. We will collect a Resonance Raman Spectroscopy (RRS) assessment from children at the beginning and end of the school year as well. RRS is an optical scan of the hand to assess carotenoid intake from fruits and vegetables. It has been used safely in prior studies with children aged 3 and older. We expect to collect this information from up to 820 children between the ages of 3 and 5.

Risks and Benefits

As in all research, there exists the potential risk to study participants is the potential for loss of confidentiality. Measures to protect the confidentiality of study participants will be implemented as described in the Data Handling and Recordkeeping section below. No physical risks related to participation in this study are foreseen. Some educators may experience discomfort as a result of answering questions that they consider personal in nature. This risk will be minimized by their ability to withdraw from the study

Study Title: Developing and Testing Implementation Strategies for Evidence-Based Obesity Prevention in Childcare
PI: [name]
Institution: University of Arkansas for Medical Sciences
Support: NIH K01 DK110141-01, Arkansas Biosciences Institute (FUNDED)
NIGMS COBRE Center for Childhood Obesity Prevention (FUNDED)
or to refuse to answer any question which makes them uncomfortable.

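### Panel staff who build and revise the enhanced strategy are not kept out of the basic arm, so the control condition can be contaminated

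*Combined protocol and SAP*

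**What the plan says.** Two sections of the combined protocol and SAP describe who sits on the panel.

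- Study Design and Procedures, Aim 2: "The EBQI Panel will include teachers and directors from representative sites that will implement the enhanced strategy in Aim 3". The same paragraph gives the size: "We expect to recruit an EBQI panel of 10 stakeholders". It also mentions parents and at least one teacher with earlier WISE experience.
- Study Population, Inclusion, and Exclusion, Aim 2: stakeholders come from "sites that will implement WISE in Aim 3", from sites with earlier WISE experience, and from Head Start parents. No arm is named.

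The Aim 3 procedures cover allocation. Of the teacher survey completed before the spring 2018 mealtime observations, they say: "This information will be used to inform stratified randomization to treatment conditions (basic or enhanced". On the unit, they say: "Classrooms will be randomized to participate in either the basic (i.e., control) or enhanced implementation of WISE". The agency has 12 sites and 38 classrooms. The Study Population section adds, for Aim 3: "Because the program is now adopting the WISE curriculum in all agency classrooms, WISE lessons are a part of normal educational activities". Implementing WISE therefore describes both arms.

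The Aim 3 procedures also have the panel meet after the Fall and Winter fidelity rounds. It reviews interview themes and the fidelity seen so far, and its feedback shapes changes to the enhanced strategy for the rest of the year. The Data Analysis section for Aim 3 specifies fixed terms for intervention and time and random effects for classroom and teacher. It does not mention panel membership.

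**The concern.** The panel creates the treatment under test. If its teachers may come from either arm, some control classrooms are led by people who helped design the enhanced package. If its directors may come from any site, some oversee basic and enhanced classrooms side by side. During the year the same people would see interim fidelity, which is the Implementation outcome in Table 1, and would discuss how to raise it.

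A basic-arm panel teacher does not receive the control condition as defined, which is a 6-hour training and a monthly newsletter. The panel is planned as 8 sessions of 1 to 2 hours (6 to 8 meetings in the Study Population section). That is more contact with the enhanced strategy than is trivial. The likely effect is to raise fidelity in some basic classrooms and shrink the difference between arms. With only 38 classrooms, in a pilot meant to inform a later definitive trial, even a modest unrecorded dilution matters.

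**Working it through.** The plan gives no figure on this point, so there is nothing to reproduce. The check compares the sections and then sizes the possible exposure.

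**Sections side by side.** The Aim 2 procedures name sites that will have the enhanced strategy. The Study Population section names any Aim 3 WISE site, which means every agency site. The Aim 3 text speaks of randomisation in the future tense while reporting in the past tense a panel decision about champions. This suggests that panel work came first, but no section dates allocation relative to panel recruitment. No section says what happens to a panel member allocated to basic, or limits the fidelity data shown by arm.

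**Inputs.** From the documents: 38 classrooms, 12 sites, about 10 panel members. Assumed, because not stated: 1:1 allocation (19 per arm), no stratification in the calculation, and k = 3 to 5 panel members who teach in separate Aim 3 classrooms.

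**Can chance keep panel teachers out of the basic arm?** P(all k enhanced) = C(38−k, 19−k) / C(38, 19).
- k = 3: 11.5%, so at least one is in basic with probability 88.5%.
- k = 5: 2.3%, so at least one is in basic with probability 97.7%.

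Some Aim 3 wording refers to enhanced sites. If whole sites were allocated 6:6, P(all k panel sites enhanced) = C(12−k, 6−k) / C(12, 6), which is 9.1% for k = 3 and 0.8% for k = 5. The conclusion is the same.

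**Directors.** A site has on average 38/12 = 3.2 classrooms. For a site with 3 classrooms, P(both arms present) = 1 − 2 × 0.115 = 77%. A panel director would usually oversee both arms.

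**Expected dilution through teachers.** The expected number of panel classrooms in basic is k/2, so 1.5 to 2.5. As a share of the basic arm, f = 1.5/19 = 8% to 2.5/19 = 13%. If those classrooms gain a fraction e of the enhanced effect Δ, the expected contrast is Δ(1 − f·e).
- e = 1 (full exposure): 8% to 13% dilution.
- e = 0.5: 4% to 7% dilution.

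These are averages over the randomisation. The realised count can be higher: all five in basic would be 5/19 = 26%, with probability 2.3%. Exposure through directors is not included, because the documents do not give the number of directors on the panel.

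**The case against.** Developing and refining a strategy with local implementers is the declared method, in a pilot with formative evaluation, and in-trial changes are confined to the enhanced strategy. The two descriptions of the panel need not conflict, since enhanced sites are a subset of WISE sites. Panel attendance also gives a teacher neither a site champion nor the champion's facilitator contact at least monthly, so full exposure is implausible. All of this stands. It limits the size of the problem and makes full exposure a ceiling. It does not remove the gap, because panel staff are still not separated by arm.

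A reader might infer more: that naming enhanced sites in Aim 2 means allocation was pre-set and motivated classrooms were placed in the enhanced arm. The documents do not support that.
- The Aim 3 procedures and the Study Population section state randomisation, and the procedures call it stratified.
- The order of panel seating and allocation is inferred from the aim sequence and verb tense.
- With classroom randomisation, a site with 3 classrooms has at least one enhanced classroom with probability 1 − 0.115 = 88.5%, so the Aim 2 sentence can hold for most sites with nothing pre-set.
- A panel drawn from an arm that had already been randomised would not select classrooms into it.

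An inflation figure would need an assumed motivation effect for which the documents give no basis.

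**Conclusion.** The concern holds as a contamination risk, not as evidence of pre-set allocation. As written, the plan allows basic-arm teachers and directors of mixed sites to help build the enhanced package, to see interim fidelity and to help revise the package during the year. The analysis has no means of showing the effect.

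The direction is most likely dilution. The size is unknown. An expected 8% to 13% is the upper limit through teachers, given 3 to 5 panel teachers, 1:1 classroom allocation and full exposure. Partial exposure makes it smaller. Panel directors, or an unlucky allocation, could make it larger. This is an inexpensive improvement to make and does not undermine the trial.

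**What to change.** 1. Reconcile the Aim 2 procedures with the Study Population section. State when allocation takes place relative to panel recruitment, and that it ignores panel membership.
2. Record panel membership, from the panel roster if allocation has already happened. Pre-specify one sensitivity analysis that excludes panel teachers' classrooms in both arms. Treat exclusion of panel directors' sites only as a secondary exploratory check.
3. Limit the in-trial panel meetings, and the interim fidelity data shown there, to members with no current basic-arm classroom: enhanced-arm teachers, parents, and staff with earlier WISE experience who are not now in the basic arm. The last condition is needed because the Ethical Considerations section says that WISE was previously offered in some of the agency's own sites. Show any director of a mixed site enhanced-arm data only.

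**Cost.** There would be a wording change, one recorded variable, one added analysis and fewer voices at the in-trial meetings. Dropping 3 to 5 of 38 classrooms widens intervals by roughly √(38/35) to √(38/33), or 4% to 7%, if precision scales with the number of classrooms. Each director's site removes about 3 classrooms. Three such sites would remove about 9.5 of 38, a quarter, which is why that check stays exploratory. Exposure during Aim 2 development cannot be undone and should be reported as a limitation.
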